15.2.3.3 Demographic and Baseline Characteristics

Demographic and Baseline characteristics will be analysed in a descriptive fashion and results will be presented overall and by treatment group.

15.2.3.4 Subject Disposition

The following will be summarised (overall and by treatment group where applicable):

- Subjects screened
- Subjects randomised
- Subjects treated
- Subjects in each analysis set
- Subjects completing the study/withdrawing early (including withdrawal reason)
- Subject allocation by study site

15.2.3.5 Evaluation of Primary Efficacy Variables

For analysis of the primary efficacy variables, an analysis of covariance (ANCOVA) model will be used to assess the change in ADCOMs/ADAS-Cog v14 score from Baseline (Week 0) to Week 12/EOT. Treatment group will be used as fixed effect and the baseline value as a covariate. For both primary efficacy variables, the following hypotheses will be tested:

$$H_0: \mu_P \leq \mu_X \text{ vs. } H_1: \mu_P > \mu_X,$$

where μ_P and μ_X denote the change from Baseline to Week 12/EOT in ADCOMs and ADAS-Cog v14 for the placebo and Xanamem™ treatment groups, respectively. Both tests will be performed at a type I error rate of 0.05 one-sided, with a priori hierarchical handling of multiplicity, as described above, based on the least squares means (LS means) for the change from Baseline to Week 12/EOT. LS means from the ANCOVA will be used to derive 90% and 95% confidence intervals. The primary efficacy analysis will not replace missing Week 12/EOT.

The analysis described above will be repeated on the PP set for supportive evidence.

Sensitivity analyses aim at assessing the robustness of the primary efficacy analysis. The following two analyses will be performed:

- An additional ANCOVA, imputing missing Week 12/EOT data based on resampling from the placebo subjects, taking baseline values into account
- An additional ANCOVA, adding site as a factor. Sites contributing few subjects may be pooled. Any decision on pooling sites will be undertaken before unblinding.

Whilst the European Medicines Agency discussion paper⁴⁰ foresees the use of the linear models for sensitivity analyses, complementing different methods of primary analyses, the type and order of analyses in this study – ANCOVA as primary efficacy analysis and placebo-based imputation as sensitivity analysis – are chosen in a different fashion due to the following reasons:

- The development stage this study is associated with, where the primary aim is to explore a possible therapeutic effect of Xanamem™; in conjunction with
- The relatively short study duration which can be expected to reduce the number of missing values in either treatment group and
- The fact that the primary efficacy variables will only be assessed at Baseline and Week 12/EOT.

15.2.3.6 Evaluation of Secondary Efficacy Variables

Secondary efficacy variables will be analysed in a descriptive manner. Summary statistics will be presented overall and by treatment group, and an exploratory comparison will be performed between the two treatment groups.

RAVLT: Results will be described for each visit as actual values and change from Baseline. An exploratory ANCOVA will be performed on the change from Baseline to Week 12/EOT for comparison between the treatment groups, including treatment group as fixed effect, and the baseline value as a covariate.

CDR-SOB: Results will be described for each visit as actual values and change from Baseline. An exploratory ANCOVA will be performed on the change from Baseline to Week 12/EOT for comparison between the treatment groups, including treatment group as fixed effect and the baseline value as a covariate.

MMSE: Results will be described for each visit as actual values and change from Baseline. An exploratory ANCOVA will be performed on the change from Baseline to Week 12/EOT for comparison between the treatment groups, including treatment group as fixed effect and the baseline value as a covariate.

NPI: Results will be described by domain for Baseline and last visit. An exploratory ANCOVA will be performed on the change from Baseline to Week 12/EOT for comparison between the treatment groups, including treatment group as fixed effect. Sub-group analyses will be performed for subjects with (score > 1) and without (score 0 to 1) symptoms at Baseline if warranted by the number of subjects in each treatment group and sub-group.

NTB – Executive Domain (COWAT and CFT): Results will be described for Baseline and last visit. An exploratory ANCOVA will be performed on the change from Baseline to Week 12/EOT for comparison between the treatment groups, including treatment group as fixed effect, and the baseline value as a covariate. In addition to the composite score, independent components will be analysed.

15.2.3.7 Evaluation of Safety Variables

Clinical safety laboratory data: clinical safety laboratory data will be presented by treatment group and overall. For each visit, the actual result and the change from Baseline will be presented. Count and shift tables for values outside the normal ranges will be presented as appropriate. In addition, individual listings will be provided for subjects with at least one value outside the normal range for a given laboratory parameter.

AEs: TEAEs will be described using descriptive statistics, and coded according to the Medical Dictionary for Regulatory Activities (MedDRA) system organ class and MedDRA preferred term, by treatment group and overall for the following categories:

- All TEAEs
- Treatment-emergent AESI
- Treatment-emergent SAEs

- TEAEs by severity
- Drug-related TEAEs
- TEAEs leading to temporary or permanent discontinuation of study drug
- TEAEs leading to study discontinuation

ECG: The results for the ECG will be presented by treatment group and overall. For each visit, the actual results and the change from Baseline will be presented.

CSSRS: Suicidal ideation, suicidal behaviour and self-injurious behaviour without suicidal intent, as well as suicide-related TEAEs based on the CSSRS during treatment, will be tabulated by treatment group and overall. Shift tables by treatment group will be prepared for changes in CSSRS categories from Baseline to during treatment, as well as for the maximum suicidal ideation score. In addition, individual listings will be provided for subjects with at least one occurrence of suicidal ideation, suicidal behaviour or self-injurious behaviour without suicidal intent at any time under treatment.

Vital signs: The results for vital signs will be presented by treatment group and overall. For each visit, the actual results and the change from Baseline will be presented.

Physical examination: Abnormal results will be presented by individual listings.

NFM data will be analysed in the safety data set. Variables will be presented using summary statistics according to each variable's scale and treatment groups will be compared in an exploratory fashion. Special attention will be directed at intra-subject changes over the course of the study. Count tables will be provided by treatment group and overall for subjects with a) an NTSS-6 > 6 and b) abnormal results for any sensory test from the TCNS. For each visit, the actual results and the change from status before study drug treatment will be presented.

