 - a) Inability to sense a stimulus even at the secondary (more proximal) skin area for pinprick, light touch, and vibration or temperature at the foot, in at least one extremity (in case neurography measures are normal, the case will be discussed with the ICON MM to assess subject eligibility)
 - b) Nerve conduction abnormalities beyond local normal values or inability to measure SNAP or CMAP in the primary or a secondary (back-up) nerve
 - c) NTSS-6 score > 6, but note that subjects are eligible even if they show:
 - Missing reflexes of the Achilles tendon (ankle), but a positive patellar (knee) tendon reflex
 - Missing ability to name toe or thumb position
6. Has had a stroke within the year prior to randomisation, as determined by the investigator.
7. Has a lifetime diagnosis of a major psychiatric disorder (other than dementia), based on the Diagnostic and Statistical Manual of Mental Disorders, 4th Edition criteria. This

- includes but is not limited to schizophrenia, schizoaffective disorder, bipolar affective disorder, alcohol dependence syndrome or major depressive disorder.
8. Has a history of disease directly related to the hypothalamus, the pituitary and/or the adrenal glands which affect the hypothalamic-pituitary-adrenal axis function.
 9. Has uncontrolled clinical conditions relating to glucose and lipid metabolism.
 10. Clinically significant ECG abnormalities, including QTc interval > 450 msec, following ECG tracings at Screening. A single repeat evaluation will be allowed if the investigator or designee has reason to believe the reading is faulty or to help assess the clinical significance of an abnormality. Any other ECG abnormality that is seen as exclusionary will first be discussed with the ICON MM.
 11. Use of any prohibited medication (see [Section 10.8](#) for details).
 12. Participation in another clinical study of an investigational drug or device whereby the last drug/device administration is within 60 days of Screening.
 13. Inability to communicate well with the investigator (i.e. language problem, non-fluent English [as scales will be provided in English only], poor mental development or impaired cerebral function).
 14. Subject will undergo the tests, ADAS-Cog v14, CDR-SOB, MMSE, NTB (executive domain) and RAVLT at the indicated time-points to avoid uncontrolled learning effects. Subjects who need to perform these tests externally to and in parallel with this study will be excluded.

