12.7 Nerve Function Monitoring

NFM consists of sensory testing (vibration and thermal perception), motor and sensory nerve neurography (amplitude and conduction velocity) and clinician-rated outcome in TCNS. Subject-related outcome measure, NTSS-6, is part of NFM, and is discussed in [Section 12.8](#). The aim is to detect intra-subject worsening from before treatment as an indicator for neurotoxicity. Subject total “Before Treatment” status is calculated as the average of the Screening visit and Baseline visit data. The tests will follow existing local standards and procedures, but should be run in a consistent fashion within a given site and subject to minimise intra-subject variability, e.g. constant skin temperature of the feet of at least

32°C/90°F, same assessor, same procedures, same chronological order of assessments, same time of day. Measurements will be taken twice for each assessed nerve in both the left and right extremity. The NFM can be conducted \pm 3 days of the scheduled protocol visit, except at the Baseline visit, where it must be conducted within 3 days prior to the randomisation step.

The following tests will be performed:

- Vibration detection threshold: Note that vibration is also part of the TCNS. This test will be performed with a Rydel–Seiffer graded tuning fork (64 Hz, 8/8 scale) that is placed over a bony prominence (medial malleolus) of each foot and left there until the subject can no longer feel any vibration. Threshold will be determined as a disappearance threshold with two stimuli repetitions of each foot.

Subjects with the ability to define a threshold within two assessments (even if at 1/8) will be graded “Normal=0” in TCNS. If the subject cannot discriminate such a threshold at the medial malleolus (most distal point to measure), the same exercise will be repeated with the tuning fork placed over the patella.

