7.8.4.2 Toronto Clinical Neuropathy Score (TCNS)

The neurological examination will cover all aspects of the Toronto Clinical Neuropathy Score (TCNS). Following TCNS data¹⁵ will be collected.

Symptom scores (0-6)	Reflex scores (0-8)	Sensory test scores (0-5)
Foot	Knee reflex	Pinprick
Pain	Ankle reflex	Temperature
Numbness		Light touch
Tingling		Vibration
Weakness		Position
Ataxia		
Upper-limb symptoms		
Symptom scores: present=1; absent=0.		
Reflex scores: absent=2; reduced=1, normal=0 for each side (right and left)		
Sensory test scores: abnormal (for any side, left or right)=1, normal=0		

The total TCNS score (0 – 19) is sum of all items of TCNS¹⁵.

Descriptive statistics for absolute value and absolute change from Baseline for total TCNS score will be presented for screening, Baseline, Interim (Week 4), Interim (Week 8) EOT (Week 12) and Follow-up (4 weeks post last dose of study drug) visits by treatment group and overall. The abnormal results for any sensory test from the TCNS will also be summarized by treatment group and overall for screening, Baseline (Week 0), Interim (Week 4), Interim (Week 8) EOT (Week 12) and Follow-up (4 weeks post last dose of study drug) visits. TCNS data will be listed.

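### The SAP tabulates abnormal TCNS sensory tests only as a visit-wise prevalence; add a per-test count of new abnormalities to deliver the change from pre-treatment status that the protocol promises

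*Protocol*

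**What the plan says.** Protocol 12.7 gives the purpose of nerve function monitoring (NFM): "The aim is to detect intra-subject worsening from before treatment as an indicator for neurotoxicity". The analysis text in Protocol 15.2.3.7 has three relevant parts. It says "Special attention will be directed at intra-subject changes over the course of the study". It plans count tables by arm "for subjects with a) an NTSS-6 > 6 and b) abnormal results for any sensory test from the TCNS". It then adds "For each visit, the actual results and the change from status before study drug treatment will be presented".

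SAP 7.8.4.2 turns this into two TCNS summaries plus a listing. The first is on the total: "Descriptive statistics for absolute value and absolute change from Baseline for total TCNS score will be presented for screening, Baseline" and the later visits. The second is the count: "The abnormal results for any sensory test from the TCNS will also be summarized by treatment group and overall for screening, Baseline (Week 0") and the later visits. The total is the sum of symptom scores (0–6), reflex scores (0–8) and five sensory tests scored 0 or 1 (pinprick, temperature, light touch, vibration, position). No change, shift or new-onset summary is given for the sensory tests. SAP section 10 records no changes from the protocol's methods.

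On entry, exclusion criterion 5 in Protocol 9.3.2 keeps a subject eligible despite "Missing ability to name toe or thumb position". Criterion 5a sends a subject with other sensory loss but normal neurography to discussion with the Medical Monitor.

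**The concern.** The by-visit count does not refer to the subject's own earlier result. It answers how many subjects are abnormal now, whereas the monitoring is meant to show who has got worse. A subject already scored abnormal on position who then loses vibration sense is counted once before and once after, so the count stays the same. Across a group, a new loss in one subject and a recovery in another leave it unchanged too.

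The NTSS-6 half of the same table differs. Scores above 6 are excluded at entry, so that half is close to a new-event count. The sensory half has no such protection.

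At stake is how clearly the report can show, by arm, new sensory loss in a trial that monitors nerve function for exactly this purpose. Shift tables are planned for laboratory, ECG and CSSRS results (SAP 7.8.2, 7.8.3, 7.8.5) but not for NFM (SAP 7.8.4).

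**Working it through.** **The plan's own NFM figures.** Protocol 15.1 states about 90% and more than 98% probability of seeing at least one event in 78 subjects at true rates of 3% and 5%.
- 1 − (1 − 0.03)^78 = 90.7%
- 1 − (1 − 0.05)^78 = 98.2%

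Both reproduce. They concern seeing at least one event, which is useful here only if a new abnormality can be told from one present at entry.

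**What can be scored abnormal at entry.** Under Protocol 12.5 a sensory test is normal if the quality is discriminated at least at the secondary area. For position, Table 3 gives the big toe as primary and the thumb as secondary. Failure at the toe with an intact thumb therefore scores 0. Failure at both scores 1, and criterion 5 does not exclude it. Vibration counts as normal with a threshold as low as 1/8, and with thermal discs 8 or fewer correct pairs on either foot excludes the subject (Protocol 12.7). Further entry abnormalities could come through the 5a discussion. Entry prevalence is therefore unknown and may be low.

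**Illustration of dilution.** From the documents: 78 per arm. Assumed, because the documents give no figures: entry prevalence p0; new-loss rate r (10% on Xanamem, 1% on placebo); entry abnormalities persist; new loss is independent of entry status. The one-sided 5% Fisher test is a yardstick only, since the plan calls the comparison exploratory.

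Planned count rate = p0 + (1 − p0) × r. For p0 = 5%: 0.05 + 0.95 × 0.10 = 14.5%, and 0.05 + 0.95 × 0.01 = 5.95%.

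| Entry prevalence | Xanamem | Placebo | Ratio | Power |
|---|---|---|---|---|
| 0% | 10.0% | 1.0% | 10.0 | 74% |
| 1% | 10.9% | 2.0% | 5.5 | 66% |
| 2% | 11.8% | 3.0% | 4.0 | 59% |
| 5% | 14.5% | 6.0% | 2.4 | 44% |
| 10% | 19.0% | 10.9% | 1.7 | 33% |

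A new-onset count taken per test keeps the 10% versus 1% contrast and 74% power in every row, on the simplification that a subject with one entry abnormality has the same chance of new loss on the remaining tests.

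**Sensitivity to the placebo rate.** With 10% versus 5% new loss, power is about 22.5% for new onset. At 5% entry prevalence the planned count compares 14.5% with 0.05 + 0.95 × 0.05 = 9.75%, for a power of 16%. The gain is then small and neither count is strong.

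**Where the dilution comes from.** At 5% entry prevalence, the new losses in subjects already counted number 78 × 0.05 × 0.10 = 0.39, of 78 × 0.10 = 7.8 expected on Xanamem. Most of the lost contrast is therefore background added to both arms. New cases made invisible are the smaller part.

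**The case against.** The strongest reply is that the plan does look at within-subject change.
- The protocol promises it in the sentences on either side of the count.
- The sensory table shows Screening and Baseline, so net group change can be read. The power figures above use post-treatment counts alone and ignore this.
- A new sensory loss adds one point to the TCNS total even in a subject already abnormal.
- All TCNS data are listed.
- Any NFM worsening goes to the Medical Monitor, potential signals go to unblinded review by the DSMB sub-committee, and treatment-emergent AESIs are tabulated by arm.

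All of this stands, but it leaves a gap. The protocol's promise reaches the SAP only for the total, where a one-point sensory loss can be offset by a symptom or reflex point. Screening and Baseline columns give net change, not new losses. Listings give no count by arm. A potential nerve signal under Protocol 12.7.1 needs at least two related parameters, so an isolated sensory loss may never reach the AESI table.

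A reader might infer that the plan ignores pre-treatment status, that everyone admitted with missing toe position is counted abnormal throughout, or that neurotoxicity would go undetected. The documents support none of these: the protocol commits to change from pre-treatment status, toe-only loss scores normal, and case-by-case review does not depend on this table.

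**Conclusion.** This is a completeness gap in SAP 7.8.4.2. The protocol commits to change from pre-treatment status for NFM variables. For the TCNS sensory tests the SAP delivers only a prevalence, which can be diluted by abnormalities present at entry and by recoveries.

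That the count is a prevalence follows from the text. How much it matters cannot be settled from the documents, because they give neither entry prevalence nor new-loss rates. With no scored entry abnormality and no recoveries there is no dilution. Under the assumed 10% versus 1%, power falls from 74% to 59% at 2% entry prevalence and to 33% at 10%. With a 5% placebo rate the difference at 5% prevalence is about 22.5% against 16%. The point is modest, but it is cheap to correct and bears on a stated safety aim.

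**What to change.** Keep the planned count and add one table to SAP 7.8.4.2, by arm. Per sensory test, count subjects whose test was normal at both Screening and Baseline and is abnormal after the first dose, with the number at risk. Give an overall row for subjects with at least one such test. Show it by visit and cumulatively to Week 12, with Follow-up separate.

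Requiring normal results at both pre-treatment visits also settles the reference. Protocol 12.7 and SAP 7.8.4 define pre-treatment status as the average of Screening and Baseline, SAP 7.8.4.2 uses change from Baseline, and an average of two 0/1 scores has no stated rule.

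The cost is one extra table from data already collected. Single-test changes will include measurement noise in both arms, so the table should be read as a comparison of arms. Protocol 15.2.3.7 can stay as written.

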15.2.3.8 PK/PD Modelling

Nonlinear mixed effects modelling will be utilised to develop a population PK model for Xanamem™ plasma concentrations. From this, exposure metrics will be derived which may be used subsequently to explore exposure-response relationships with selected exposure and efficacy/safety endpoints.

A separate Modelling and Simulation Analysis Plan will be prepared and results from the PK/PD modelling will be reported separately from the clinical study report.

15.2.3.9 Evaluation of Exploratory Variables

Exploratory variables will be analysed by treatment group and overall using descriptive statistics for categorical and continuous data, as applicable. For continuous data, the change from Baseline will be analysed in addition to the actual visit values; for categorical data, shift tables will be presented as appropriate.

15.2.3.10 Compliance and Exposure

Exposure will be analysed by calculating the number of days with exposure to study drug. Results will be presented overall and by treatment group.

Compliance will be analysed by calculating the ratio between the actual intake of study drug as documented by dispensed and returned study drug and the expected intake of study drug according to the treatment schedule. The percentage compliance will be described overall and by treatment group, and the number of subjects with a compliance < 80%, between 80% and 120% and > 120% will be presented by treatment group and overall.

15.2.3.11 Interim Analysis

There is one planned interim analysis after 50 completed subjects. The following endpoints will be analysed in this interim analysis:

Efficacy:

- ADAS-Cog
- MMSE
- CDR-SOB
- ADCOMS
- RAVLT
- NPI
- NTB – Executive domain (COWAT and CFT)

Safety:

- Laboratory values
- Incidence of AEs
- NFM

PK/PD:

- Plasma concentrations of Xanamem™

Evaluation of efficacy evaluables will be conducted as described in [Sections 15.2.3.5](#) and [15.2.3.6](#). For control of the type I error rate, the Haybittle-Peto approach will be used, thus setting the stopping boundary for the primary efficacy variables at a one-sided 0.001, leaving the full type I error rate of a one-sided 0.05 for the final analysis. Full details of the interim efficacy analysis will be specified in the SAP.

This interim efficacy analysis aims at providing additional information on the efficacy parameters to the DSMB, including both descriptive and inferential statistics. No study adaptations are planned based on these analyses. Should there be evidence of an overwhelming effect, the DSMB may recommend stopping early for success. Further details will be available in the DSMB Charter.

15.2.4 Data Safety Monitoring Board

A DSMB consisting of two sponsor-independent clinical experts and one sponsor-independent statistical expert will be established. The DSMB will periodically meet for the review of accumulating study data, including safety (AE and laboratory data), PD data and NFM data, and will also be involved in the interim efficacy analysis.

The DSMB will have access to unblinded data.

The DSMB will make recommendations for the remaining part of the study (further details will be provided in the DSMB Charter). The DSMB may recommend to continue with the study as planned, stop the study for early safety reasons, or judge if the dose is in any way problematic for this subject population and determine if dose modification is needed.

The DSMB will submit its recommendations in writing to Actinogen Medical who are responsible for responding to the recommendations of the DSMB and taking appropriate action. The investigators will only be informed by Actinogen Medical/ICON if the study is stopped or if additional PD subjects need to be enrolled. The DSMB may choose to make additional evaluations at any time if they feel this is warranted from a safety point of view.

The DSMB will also review unblinded PD data, available at the time of the interim analysis, of the subjects enrolled into the main study, who also volunteer to take part in the sub-study, to determine whether enough samples were collected from subjects on active drug. The PD sampling in this study will complement the previously reported Phase I data, in which most of the subjects were male and only a small number of subjects were aged 50 years or older.

The interim efficacy analysis aims at providing additional information on the efficacy parameters to the DSMB. No study adaptations are planned based on these analyses. Should there be evidence of an overwhelming effect, the DSMB may recommend stopping early for success. For control of the type I error rate, the Haybittle-Peto approach will be used, thus setting the stopping boundary at a one-sided 0.001, leaving the full type I error rate of a one-sided 0.05 for the final analysis.

The DSMB will act according to its own written SOP described in a charter and will prepare written minutes of its meetings. The Charter of the DSMB will be stored in the Trial Master File. The DSMB will maintain records of its meetings and these will become part of the study file when the study is complete.

In order not to disseminate unblinded data and to ensure that all staff involved in the conduct and final analysis of the study remain blind to the data, only the members of the DSMB, the DSMB Nerve Function Monitoring sub-committee and the unblinded DSMB statistician will have access to these data.

